### **3.6.2 Adverse Events of Special/Potential Interest**

An adverse event of special/potential interest (AESI/AEPI) is one of scientific and medical interest specific to understanding of the IP and may require close monitoring and rapid communication by the investigator to the sponsor. The AESI categories for each IP can be found in protocol Section 5.3. Other categories may be added, or existing terms may be modified, as necessary. The most recent version of the AESI/AEPI preferred terms list at clinical data lock will be used to identify and categorize AESI/AEPI.

The AESIs/AEPIs, as applicable, will be summarized similarly as other AEs described in [Section 3.6.1.](#)

Immune-mediated adverse events (imAEs) for durvalumab will be automatically adjudicated per the global imAE charter. The imAEs will be summarized, including separate summaries of the number and percentage of subjects with imAEs by category, by outcome, by maximum CTCAE grade and descriptive statistics of time to onset of imAE by AESI category.

### **3.6.3 Deaths and Treatment Discontinuations due to Adverse Events**

For those subjects who died due to one or multiple AEs, the AE(s) contributing to death will be summarized.

Summaries will be provided for TEAEs resulting in permanent discontinuation of IP. Supporting listings will be provided for AEs resulting in death and AEs resulting in permanent discontinuation of IP.

### **3.6.4 Clinical Laboratory Evaluation**

Laboratory tests will be grouped according to chemistry, hematology, coagulation, and urinalysis. Listings will be provided for all laboratory results, including coagulation. For selected chemistry and hematology tests, the change in each laboratory parameter from baseline to each post-baseline scheduled visit will be summarized graphically. Descriptive statistics will be provided for the clinical laboratory results and changes from baseline by scheduled time of evaluation including minimum and maximum post-baseline values.

Laboratory parameters will be assessed at baseline as well as throughout the study. Frequencies of worst observed grade 0-4 toxicity, as defined by the NCI CTCAE v5.0, will be presented for each laboratory parameter. The analysis will present the worst grade

observed and the rates of subjects with grade 3-4 toxicity. Additionally, 2-grade shifts from baseline to worst toxicity grade will be summarized for chemistry and hematology laboratory parameters. Separate summaries indicating hyper- and hypo- directionality of change will be produced, where appropriate. Shifts from baseline relative to the normal range (low, normal, high) will also be presented.

### Liver Function Parameters

Subjects with elevated post-baseline alanine aminotransferase (ALT), aspartate aminotransferase (AST) or total bilirubin that fall into the following categories will be identified. The number and percentage of these subjects will be summarized.

Liver Function Parameters	Category
ALT	

• <math>\geq 3\times - \leq 5\times</math> ULN

• <math>> 5\times - \leq 8\times</math> ULN

• <math>> 8\times - \leq 10\times</math> ULN

• <math>> 10\times - \leq 20\times</math> ULN

• <math>> 20\times</math> ULN

AST	

• <math>\geq 3\times - \leq 5\times</math> ULN

• <math>> 5\times - \leq 8\times</math> ULN

• <math>> 8\times - \leq 10\times</math> ULN,

• <math>> 10\times - \leq 20\times</math> ULN

• <math>> 20\times</math> ULN

Total bilirubin	

• <math>\geq 2\times - \leq 3\times</math> ULN

• <math>> 3\times - \leq 5\times</math> ULN

• <math>> 5\times</math> ULN

ALT or AST	

• <math>\geq 3\times - \leq 5\times</math> ULN

• <math>> 5\times - \leq 8\times</math> ULN

• <math>> 8\times - \leq 10\times</math> ULN,

• <math>> 10\times - \leq 20\times</math> ULN

• <math>> 20\times</math> ULN

Potential Hy's law	

• (AST <math>\geq 3 \times</math> ULN or ALT <math>\geq 3 \times</math> ULN) and (Total Bilirubin <math>\geq 2 \times</math> ULN)a

ALT = alanine aminotransferase; AST = aspartate aminotransferase; ULN = upper limit of normal range.

a: Total bilirubin  $\geq 2 \times$  ULN is defined as at least one case of post-dose total bilirubin  $\geq 2 \times$  ULN occurred after ALT or AST  $\geq 3 \times$  ULN post treatment.

Subjects who meet the potential Hy's law criteria will be listed.

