## **4 MATERIALS AND METHODS**

### **4.1 Subjects**

#### **4.1.1 Number of Subjects**

Up to approximately 60 subjects per experimental treatment arm will be randomized with equal ratios to durvalumab control and each of the open experimental arms. New durvalumab combination experimental arms may be added over time following protocol-specific guidelines (see Section [1.6.3](#)) and therefore the total number of subjects randomized to the durvalumab control arm might be higher than 60 subjects. Details regarding the specifics of a new combination arm will be provided via protocol amendment. See also Section [4.6.1](#) for potential changes to the randomization scheme and changes to overall study enrollment in the control arm and the combination experimental arms during the study.

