#### Serum Chemistry

- Albumin
- Amylase
- ALP
- ALT
- AST
- Bicarbonate
- Blood urea nitrogen / urea
- Calcium
- Chloride
- Creatinine
- Gamma-glutamyl transferase
- Glucose
- Lactate dehydrogenase
- Lipase
- Magnesium
- Potassium
- Sodium
- Total bilirubin (TBL; direct bilirubin should be obtained if TBL is  $>$  ULN)
- Total protein
- C-reactive protein

ULN = upper limit of normal

**Note:** Tests for AST, ALT, ALP, and TBL must be conducted concurrently and assessed concurrently.

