#### **5.4.6 Potential Hy's Law and Hy's Law**

Cases where a subject shows elevations in liver biochemistry may require further evaluation and occurrences of AST or ALT  $\geq 3 \times$  ULN together with TBL  $\geq 2 \times$  ULN will need to be reported as SAEs. Please refer to [Appendix D](#) for further instruction on cases of increases in liver biochemistry and evaluation of Hy's Law.

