#### D 2.2 Hy's Law

AST or ALT  $\geq 3 \times$  ULN **together with** TBL  $\geq 2 \times$  ULN, where no other reason, other than the investigational product, can be found to explain the combination of increases; eg, elevated ALP indicating cholestasis, viral hepatitis, or another drug.

For potential Hy's Law and Hy's Law, the elevation in transaminases must precede or be coincident with (ie, on the same day) the elevation in TBL, but there is no specified timeframe within which the elevations in transaminases and TBL must occur.

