#### **D 4.2 Potential Hy's Law Criteria Met**

If the subject does meet potential Hy's Law criteria the investigator will:

- Notify the sponsor study representative who will then inform the study team
- Within 1 day of potential Hy's Law criteria being met, the investigator will report the case as an SAE of Potential Hy's Law; serious criteria 'Important medical event' and causality assessment 'yes/related' according to clinical study protocol process for SAE reporting

The medical monitor contacts the investigator, to provide guidance, discuss and agree on an approach for the study subjects' follow-up (including further laboratory testing) and the continuous review of data.

Subsequent to this contact the investigator will:

- Monitor the subject until liver biochemistry parameters and appropriate clinical symptoms and signs return to normal or baseline levels, or as long as medically indicated. Complete follow-up SAE Form as required.
- Investigate the etiology of the event and perform diagnostic investigations as discussed with the medical monitor.
- Complete the relevant Case Report Form (CRF) Modules as information becomes available

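### The SAP's potential Hy's law count requires bilirubin to rise after ALT/AST, while the protocol also accepts same-day elevations

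*SAP*

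**What the plan says.** SAP section 3.6.4 (Liver Function Parameters) tabulates subjects with elevated post-baseline ALT, AST or bilirubin. Its last row is potential Hy's law: ALT or AST at or above 3 × ULN and total bilirubin at or above 2 × ULN. Footnote a narrows that row. The bilirubin criterion is met only if at least one post-dose value at or above 2 × ULN has "ULN occurred after ALT or AST" at or above 3 × ULN. Subjects who meet the criterion are counted and also listed.

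Protocol Appendix D 2.1 defines potential Hy's Law by the same two thresholds. Appendix D 2.2 adds a timing rule that it applies to both potential Hy's Law and Hy's Law: "the elevation in transaminases must precede or be coincident with (ie, on the same day) the elevation in TBL". It sets no limit on the interval between the two elevations.

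Three other protocol provisions bear on the point:

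- Section 4.3.3 (Serum Chemistry): "Tests for AST, ALT, ALP, and TBL must be conducted concurrently and assessed concurrently".
- Section 5.4.6: cases with both elevations "will need to be reported as SAEs".
- Appendix D 4.2: within 1 day of the "criteria being met, the investigator will report the case as an SAE" of Potential Hy's Law.

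**The concern.** The two documents define the same safety term differently. The protocol names same-day elevations as qualifying, and the SAP's wording leaves them out. Because the four liver tests are taken at the same draw, same-day crossing of both thresholds is a foreseeable pattern.

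At stake is agreement between two parts of the study report. A subject could be reported as a Potential Hy's Law SAE and yet be absent from the table and listing that carry that name. The discrepancy can only make the SAP's count too small.

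Nothing in the SAP presents this as a deliberate choice. The version 5.0 history records edits to section 3.6.4 and explains why planned ECG and physical examination analyses were dropped, but it gives no reason for a narrower Hy's law rule.

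**Working it through.** The plan states no figure to reproduce. The check compares the two timing rules.

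**Notation.** For one subject, let T be the set of post-dose dates with ALT or AST ≥ 3 × ULN, and B the set of post-dose dates with total bilirubin ≥ 2 × ULN. Both sets are non-empty.

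**SAP footnote a.** Some b in B is later than some t in T. This is equivalent to max(B) > min(T).

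**Same-day dates included, keeping the footnote's any-value form.** Some b in B is on or after some t in T. This is equivalent to max(B) ≥ min(T).

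**Difference.** The second rule holds and the first fails exactly when max(B) = min(T), that is, when the last qualifying bilirubin is on the same day as the first qualifying ALT or AST. Since > implies ≥, no subject counted under the footnote is lost. The result does not depend on the number of draws.

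**Patterns over successive visits v1 < v2 < v3:**

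| ALT/AST ≥ 3 × ULN | Bilirubin ≥ 2 × ULN | SAP as written | Same day included |
|---|---|---|---|
| v1 | v2 | counted | counted |
| v1 | v1 only | **not counted** | **counted** |
| v1 | v1 and v2 | counted | counted |
| v2 | v1 only | not counted | not counted |
| v2 | v1 and v2 | **not counted** | **counted** |
| v2 | v1, v2 and v3 | counted | counted |

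The second row is the clear protocol case that the SAP omits. The fifth row is also added when same-day dates are included; its standing under the protocol is taken up in the objection.

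**Is a later bilirubin value bound to rescue the case?** Often, but not always. Appendix D 4.2 tells the investigator to "Monitor the subject until liver biochemistry parameters and appropriate clinical symptoms and signs return to normal or baseline levels", or for as long as medically indicated, which will tend to produce further samples. Bilirubin may still be below 2 × ULN at the next one. Scheduled chemistry is once per 28-day cycle on treatment (Protocol Table 5) and every 8 weeks or less often in follow-up (Protocol Table 6). SAP section 3.6 also disregards visits more than 90 days after the last dose.

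**Size per subject.** The documents give no expected number of cases. For the denominator, Protocol section 4.1.1 says "Up to approximately 60 subjects per experimental treatment arm will be randomized". Assuming about 60 treated in an arm, one omitted subject changes the percentage by 100 × 1/60 = 1.7 points. This is a per-case conversion and does not predict how many cases there will be.

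**The case against.** The strongest reply is that the omission depends on reading the word 'after' strictly. The footnote does not say that same-day results are excluded, the table row joins the two criteria with a plain 'and', and table specifications are left to a statistical programming plan that is not available. The author may have meant 'on or after', and the program may already do that. This stands as a limit on what can be claimed: the wording differs for certain, but an actual omission is not shown.

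A second reply concerns the onset of the elevation. If Appendix D 2.2 means that the transaminase rise must begin no later than the bilirubin rise, a subject with raised bilirubin at v1 and v2 and raised ALT first at v2 is not clearly a protocol case, yet including same-day dates would add that subject. The protocol does not settle this. It is not a reason to keep the present text, however, because the footnote already accepts any single qualifying bilirubin: it counts the same subject once bilirubin is raised at v3. Including the same day extends that existing rule and introduces no new ordering.

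Third, the case would not vanish from the report. A Potential Hy's Law SAE within 90 days of the last dose would enter the adverse event summaries, the values fall in the separate ALT/AST and bilirubin categories, and section 3.6.4 says "Listings will be provided for all laboratory results, including coagulation". This is correct and is a main reason for rating the point minor.

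Finally, including the same day would not align the documents fully. Appendix D 2.1 covers any time in the study after the start of investigational product, while SAP section 3.6 stops 90 days after the last dose. That is a separate difference and would remain.

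**Conclusion.** The concern holds, as a minor point. As written, footnote a is narrower than Appendix D 2.2. It leaves out a subject whose only bilirubin ≥ 2 × ULN falls on the day of the first ALT or AST ≥ 3 × ULN, although the protocol counts that subject and requires an SAE report. No other SAP text corrects this.

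The consequence is confined to one safety count and one listing, and no efficacy result or stopping rule uses them. The number affected cannot be worked out from the documents and may be zero. The conclusion rests on a literal reading of the footnote.

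**What to change.** In footnote a, replace 'after' with 'on the same day as, or after', and leave the rest unchanged. Do not add an ordering by first elevations, which the protocol does not state.

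The cost is one phrase in the SAP. In the program, the date comparison should be ≥; if it is already coded that way, only the text changes. No subject now counted would be lost.

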### Assessment of Nephrotoxicity

Creatinine clearance rate ( $C_{Cr}$ ) will be calculated using serum creatinine ( $S_{Cr}$ ) in mg/dL and the Cockcroft-Gault formula to estimate glomerular filtration rate (GFR), defined as follows:

$$C_{Cr} (\text{mL/minute}) = \{((140 - \text{age}) \times \text{weight})/(72 \times S_{Cr})\} \times 0.85, \text{ if female}$$

A shift table from baseline to “worst-case” on treatment  $C_{Cr}$  value will be provided. Baseline and “worst-case” on treatment  $C_{Cr}$  value will be categorized as follows:

- Normal:  $\geq 90$  mL/min
- Mild Impairment:  $\geq 60 - < 90$  mL/min
- Moderate Impairment:  $\geq 30 - < 60$  mL/min
- Severe Impairment:  $\geq 15 - < 30$  mL/min
- Kidney Failure:  $< 15$  mL/min

### **3.6.5 Other Safety Evaluations**

#### **3.6.5.1 Vital Signs**

Vital signs will be assessed at baseline and throughout the study. Vital signs will be summarized by study visit which will include descriptive statistics for the value of the parameters and the changes from baseline to post-baseline scheduled visits. Minimum and maximum post-baseline values will also be summarized..

#### **3.6.5.2 Electrocardiogram**

No electrocardiogram analyses are planned. ECGs were only collected prior to study treatment initiation.

#### **3.6.5.3 Eastern Cooperative Oncology Group Performance Status**

Eastern Cooperative Oncology Group (ECOG) performance status will be assessed at baseline as well as throughout the study. ECOG will be summarized for baseline and the “worst” case including descriptive statistics for the value of the parameters and the shift table from baseline to the “worst” performance post-baseline.

#### **3.6.5.4 Physical Examinations**

No physical examination analyses are planned.

### **3.6.6 Subgroup Analyses**

No subgroup analyses are planned.

### 3.7 Immunogenicity

Immunogenicity results will be summarized for the As-treated population. Number and percentage of subjects in the following categories will be provided.

- ADA positive at baseline and/or post-baseline visits.
- Persistent positive, defined as positive at  $\geq 2$  post-baseline assessments (with  $\geq 16$  weeks between first and last positive) or positive at last post-baseline assessment.
- Transient positive, defined as negative at last post-baseline assessment and positive at only one post-baseline assessment or at  $\geq 2$  post-baseline assessments (with  $< 16$  weeks between first and last positive).
- Treatment-boosted, defined as baseline positive ADA titer that was boosted to a 4-fold or higher-level following drug administration.

Similarly to safety analyses, only post-baseline visits up to and including 90 days following the date of last dose of study medication will be considered when deriving the categories. Study discontinuation blood samples will be summarized at the closest nominal time point that does not already have a value. All subjects with titer information will be shown in data listings.

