**Table 2 Secondary Objectives and Associated Endpoints**

| Type           | Objective  | Endpoint   |
|----------------|--|--|
| Immunogenicity | (a) To assess the immunogenicity of durvalumab alone or in combination with novel agents | ADA incidence of durvalumab or novel biologic agents |
|                | (b) To assess the immunogenicity of novel biologic agents in combination with durvalumab |  |

ADA = antidrug antibody; AE = adverse event; DC = disease control; DoR = duration of response; OS = overall survival; PFS = progression-free survival; PFS-12 = progression-free survival 12-month landmark rate; PK = pharmacokinetic; RECIST v1.1 = Response Evaluation Criteria for Solid Tumors version 1.1 SAE = serious adverse event.

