#### **4.8.5 Analysis of Immunogenicity/Pharmacokinetics**

##### **Immunogenicity**

Only subjects who receive at least 1 dose of durvalumab and/or other combination study drug, and provide at least 1 post-treatment sample, will be evaluated. For each treatment arm, the immunogenic potential of durvalumab will be assessed by summarizing the number and percentage of subjects who develop detectable ADAs to durvalumab. For experimental arms that

include a biologic agent, the immunogenic potential of the combination study drug will be assessed by summarizing the number and percentage of subjects who develop detectable ADAs to the combination study drug.

The impact of ADAs on PK and safety will be assessed if data allow. Samples confirmed positive for ADAs may also be evaluated for neutralizing antibody activity.

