**Table 3.2-1      Analysis Populations**

Population	Description
Intent-to-treat (ITT) Population	The ITT population includes subjects who are randomized. Subjects will be analyzed according to their randomized treatment group.
As-treated Population	The As-treated population includes all subjects who receive any IP. Subjects will be analyzed according to the treatment they really receive.
Response-evaluable Population	The Response-evaluable population includes subjects from the As-treated population who have a baseline disease assessment (DA), have the opportunity to be followed for at least 16 weeks at the time of the DCO (i.e., dosed at least 16 weeks prior to the time of the DCO), and either has at least one post-baseline disease assessment and/or discontinued treatment due to death or disease progression. The response-evaluable population will not be used for the final analysis.

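### No ADA category in SAP 3.7 requires a negative baseline, so the listed counts do not determine the protocol's ADA incidence endpoint

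*SAP*

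**What the plan says.** Protocol Table 2 gives the secondary immunogenicity endpoint as "ADA incidence of durvalumab or novel biologic agents". Protocol 4.8.5 says how it is assessed: the "number and percentage of subjects who develop detectable ADAs to durvalumab", with a parallel sentence for the combination drug in arms that include a biologic. The same section fixes who is counted: "Only subjects who receive at least 1 dose of durvalumab and/or other combination study drug, and provide at least 1 post-treatment sample, will be evaluated".

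SAP 3.7 sets the population differently: "Immunogenicity results will be summarized for the As-treated population". SAP Table 3.2-1 defines that population without reference to ADA samples: "The As-treated population includes all subjects who receive any IP". SAP 3.7 then lists four categories:

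- "ADA positive at baseline and/or post-baseline visits";
- persistent positive (positive at the last post-baseline assessment, or at two or more spanning at least 16 weeks);
- transient positive (negative at the last post-baseline assessment, with one earlier positive or several within less than 16 weeks);
- treatment-boosted (positive at baseline, with at least a 4-fold rise in titer after dosing).

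Post-baseline results count only up to 90 days after the last dose.

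**The concern.** Incidence concerns antibodies that appear after treatment starts. The first SAP category mixes subjects who were positive before any drug with those who turned positive later. Persistent and transient look only at post-baseline results. Boosted is confined to subjects who were already positive. No category isolates the subject who was negative at baseline and positive afterwards.

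A report that follows SAP 3.7 as written could therefore present pre-existing reactivity as persistent immunogenicity of durvalumab, oleclumab or monalizumab, and need not contain the percentage that the protocol names as a secondary endpoint.

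The population raises a second, smaller question. The SAP defines a PK-evaluable set that requires a post-baseline concentration, but no ADA counterpart, and SAP 3.7 does not carry over the protocol's sample condition.

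**Working it through.** The plan gives no ADA rate, precision or sample size for this endpoint, so there is no figure to reproduce. The check is logical, with illustrative arithmetic. The arm size of 60 is from SAP 2.4; every other count below is an assumption.

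**1. Baseline condition in each SAP category**

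| SAP 3.7 category | Baseline status required |
|---|---|
| Positive at baseline and/or post-baseline | None |
| Persistent positive | None |
| Transient positive | None |
| Treatment-boosted | Positive |

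A subject positive at baseline and at every later sample, with no rise in titer, is positive at the last post-baseline assessment and so is persistent positive.

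**2. What persistent plus transient adds up to.** Protocol Table 5 has 28-day cycles and predose ADA samples at Cycles 2, 7 and 11, which is about weeks 4, 24 and 40: (2−1)×4, (7−1)×4 and (11−1)×4. Across all positive/negative sequences over one to three of these samples, every sequence with at least one positive fell into exactly one of the two classes. So, with P persistent and T transient, P + T is the number of subjects with any post-baseline positive, whatever their baseline.

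**3. What is missing.** Let I be the number newly positive and B the number positive both at baseline and afterwards. Then

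I = P + T − B.

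B is not listed. Boosted subjects are only part of B, so the listed counts give no more than 0 ≤ I ≤ P + T − boosted. The first category equals P + T plus the baseline-positive subjects with no later positive, so it does not supply B either.

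**4. Two arms with the same SAP output.** In each arm of 60, 51 subjects are negative throughout, 4 are baseline-negative with no post-treatment sample, and 5 are positive post-baseline (3 persistent, 2 transient, 0 boosted).

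| | Arm X: the 5 were baseline-negative | Arm Y: the 5 were baseline-positive, unchanged titer |
|---|---|---|
| Any positive | 5 | 5 |
| Persistent / transient / boosted | 3 / 2 / 0 | 3 / 2 / 0 |
| Subjects who developed ADAs | 5 | 0 |
| Protocol percentage (denominator 51 + 5 = 56) | 5/56 = 8.9% | 0/56 = 0% |

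**5. Effect of baseline positives on the first category.** Take 5 newly positive subjects and add 2, 4 or 6 others who were positive at baseline. The category gives 7/60 = 11.7%, 9/60 = 15.0% or 11/60 = 18.3%, against 5/60 = 8.3% for the new positives alone.

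**6. Effect of the sample condition.** If 3, 6 or 9 of the 60 have no post-treatment sample, the protocol's denominator gives 5/57 = 8.8%, 5/54 = 9.3% or 5/51 = 9.8%, against 5/60 = 8.3% if all treated subjects were used. Such subjects can arise. Someone who stops before Cycle 2 has no on-treatment post-dose sample, and the scheduled follow-up samples (10 months and Month 15, Protocol Table 6) would fall outside the 90-day window. A discontinuation sample, which SAP 3.7 allows for, would fill the gap.

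**The case against.** Four arguments have weight.

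**The table shells may resolve it.** SAP 1 says a separate statistical programming plan holds templates for the whole SAP. The first category could be laid out as baseline, post-baseline and both, and the newly positive would then follow by subtraction. The SAP text does not exclude this, but it does not require it either. A secondary endpoint should be fixed in the SAP itself. Titers and original data are to be listed, so the split could be recovered by hand; that is a fallback, not a planned summary.

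**The denominator is not actually stated.** A reader might infer that every treated subject is in the denominator and that those without a post-dose sample count as not positive. The documents do not establish this. SAP 3.7 names a population and gives no rule for missing samples, while SAP 3.1 generally drops subjects with missing data from a summary. That rule could remove unsampled subjects from the persistent and transient rows. It does not clearly do so for the first category, where a subject with only a baseline sample still has data. What stands is that the protocol's condition is not applied in SAP 3.7.

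**No category is called the headline.** The four are listed in parallel, and the first openly includes baseline. It would be wrong to say that the SAP reports prevalence under the name of incidence. What stands is that none of the four is the incidence.

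**The protocol does not define developing ADAs by baseline status.** It leaves further detail to the SAP. Reading the word as negative before and positive after is the ordinary sense, but it is a reading. The SAP version history gives no reason for choosing different categories, although version 5.0 does explain other differences from the protocol (ECG and physical examination).

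**Conclusion.** The concern holds, within limits. The four categories in SAP 3.7 do not determine the number of subjects who developed ADAs, and the persistent-positive rule places unchanged pre-existing reactivity among the persistent positives. This follows from the definitions alone. The post-treatment-sample condition of Protocol 4.8.5 is also absent from SAP 3.7 and is only partly covered by SAP 3.1.

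The size depends on how many subjects are positive at baseline, which the documents do not say. With no baseline positives, P + T equals the number newly positive and only the denominator question remains: at most 1.5 percentage points in the illustration (9.8% − 8.3%). With 2 to 6 baseline positives in 60, the first category exceeds the new-positive percentage by 3.4 to 10.0 points (11.7% − 8.3% and 18.3% − 8.3%).

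A reader might also infer that these errors differ between arms because the arms stop dosing at different rates. No discontinuation rates by arm are given, so that remains a possibility only. The endpoint is descriptive: no hypothesis test is attached to it, and the Go/No-Go rules use DCR and ORR. The change is worth making because a named secondary endpoint is otherwise not specified.

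**What to change.** In SAP 3.7:

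1. Add treatment-induced ADA (negative at baseline, at least one positive post-baseline result), by arm and by analyte, and name it as the incidence measure.
2. Report treatment-boosted and baseline prevalence on separate rows. If a treatment-emergent total is wanted, label it as induced plus boosted: boosted subjects were already positive, so counting them as incidence goes beyond the protocol's wording.
3. Apply persistent and transient to treatment-induced subjects, or split both by baseline status.
4. State the denominator as subjects with at least one dose and at least one post-treatment ADA sample. Say how subjects without a baseline result are handled; the protocol does not require one, so excluding them would be an added condition and should be declared as such.

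The cost is SAP wording and programming. The Cycle 1 predose sample (Protocol Table 5) and the titer assay (Protocol 4.3.5) are already planned, so no new data are needed.
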